**CCDLT Study: Crossover Study – Analysis of Primary and Secondary Outcomes**

**Statistical Methods:**

In order to analyze the 2 x 2 crossover design for mainly the primary outcome, VAS, and secondary outcomes (CISS, CLDEQ, autorefraction, phoria), we utilized mixed model analysis, allowing the sequences of each subject to be modeled as repeated measures within PROC Mixed. We did not have period effects since there was no gap or wash-out period between the sequences. We obtained least-squares adjusted means from these and compared the difference between these as well. We also utilized two-sample two-sided t-tests when comparing certain secondary outcomes (pupil size, accommodation, logMAR, NRA, PRA) between lens preference at specific time points and/or between lens types. We utilized a 10% level of significance. SAS Version 9.4 was used for all analyses.

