Connecting Contact Lenses and Digital Technology

PROTOCOL

Principal Investigator: [name], OD FAAO

Sub-Investigators: [name], OD FAAO; [name] OD MD MS FAAO; [name]
MCOptom MS PhD FAAO

Study Coordinators: [name], BOptom BS; [name] BS

Site: SUNY College of Optometry, [name]

[contact] | [contact]

I. STUDY OBJECTIVES

This study seeks to address whether or not multifocal contact lenses may be a beneficial option for pre-presbyopic patients complaining of eye strain and visual discomfort while using digital devices. The primary outcome measure will be change in average score on a ten question Visual Comfort Survey using a Visual Analogue Scale (VAS) technique from baseline to day 7. Secondary outcome measures include lens preference based on a two-alternative forced choice survey, symptom changes based on the Convergence Insufficiency Symptom Survey (CISS), symptom changes based on the Contact Lens Dry Eye Questionnaire-8 (CLDEQ-8), and objective measures of binocularly and accommodation.

II. BACKGROUND AND RATIONALE

American Millennials spend an average of 18 hours a day consuming media¹ on smartphones, digital tablets and home computers – often multiple forms simultaneously. The visual demands of this type of work are unique and require the use of prolonged intermediate vision. For contact lens-wearing young adults, correcting for this working distance before the onset of presbyopia may contribute to less eye strain and visual discomfort.

Recent studies researching contact lens discomfort have attributed symptoms to a myriad of issues from undiagnosed accommodative-binocular disorders, to ocular surface disease, to the angle of computer screens.^{2,3} There is no definitive evidence stating that one variable is responsible.

Meanwhile, the number of symptomatic patients is growing. Although “occupational” spectacles are a growing trend, there appears to be no contact lens recommendation for symptomatic patients.

III. STUDY METHODOLOGY

a. Study Design and Intervention

This is a prospective, single site, randomized, double-masked, crossover pilot study. Subjects will be randomized in a 1:1 ratio based on a randomization schedule according to sequentially assigned subject numbers to either the test or control group at the first visit. Subjects will crossover at the second visit. There will be an equal number of subjects in each group.

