This study will evaluate the ability of multifocal contact lenses to decrease signs and symptoms of asthenopia for non-presbyopic patients with prolonged near and intermediate work (at least 6 hours) on digital devices. After informed consent, baseline testing will be performed to confirm an appropriate ocular health and refractive state and subjects will be screened for vergence disorders for which a near addition would be contraindicated. Symptoms will be measured by administering the CISS⁴ and CLDEQ-8.⁵ Subjects will also complete a 10-question VAS survey regarding subjective visual comfort at the baseline visit, at the end of day 1 and day 3 (via home diary), and at the follow-up visit at day 7. At the end of the study, subjects will be asked their preference in a two-alternative forced choice format.

b. Study Lenses

Johnson and Johnson 1- Day Acuvue Moist Brand spherical and multifocal contact lenses will be used (Table 1). According to recent research,⁶ the preferred viewing distance on digital devices for a similar

age group was 63 cm which would require an add of +1.59 D. A low add yielding up to +1.25 add was selected to provide an intermediate near addition without compromising distance vision as much as would be expected with higher add powers.

The site study coordinator will mask (over-label) the contact lens foils so that both examiners and subjects remain masked. The lens power (distance only), will be transcribed on the new label and the lens lot number, and expiration date will be kept in a linking log by the unmasked coordinator. The unmasked team member will assign a group number, "A" or "B" to match the randomization order for the multifocal from single vision lenses so that the examiners may dispense lenses while remaining masked.

Table 1. Study lenses

Brand	Base Curve	Diameter	Power	Add
1-Day Acuvue Moist Multifocal	8.4	14.3	Vertexed, spherical-equivalent of manifest refraction	LOW (up to +1.25)
1-Day Acuvue Moist	8.5	14.0		None

c. Sample selection

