Up to 45 subjects may be enrolled in the study to provide at least 30 evaluable subjects (allowing for up to a 33% screen failure, drop-out, or poor or missing data). A total of 30 subjects will be randomized to begin with either multifocal or single vision distance contact lenses. Subjects will wear the lenses on a daily-wear, daily-disposable schedule. Following one week (\pm 2 days) of lens wear, subjects will be evaluated and the alternate lenses dispensed. The sample size was based on previous publications studying subjective and objective outcomes with multifocal and single vision contact lenses.^{7,8} Expectations for normal distributions of data and the ability to use parametric tests are generally met with sample sizes of about 30.

d. Inclusion Criteria:

- 18 to 35 years of age
- Spectacle prescription of -0.75 to -6.00 D sphere with no more than 0.75 diopters of refractive cylinder
- Current single-vision soft contact lens wearer
- Monocular acuity of 20/25 or better in each eye (Snellen)
- Self-reported minimum of 6 hours a day on digital devices
- Self-reported complaint of eyestrain on digital devices
- No ocular pathology and/or history of eye surgery
- No history of strabismus or strabismus surgery
- No gas permeable lens wear for at least 3 months
- Subjects may not be optometrists, opticians or optometry students

Following consent, subjects will be screened further in order to exclude those with ocular surface disease and/or binocular disorders that would not benefit from a near addition.

e. Exclusion Criteria:

- Corneal staining, blepharitis and/or MGD worse than Grade 2 using the Efron Grading Scale⁹
- NRA less than +1.50 D
- Exophoria at near > 6 prism diopters¹⁰
- Vertical phoria > 1 prism diopter
- Presence of tropia
- Response of 3 or higher on question 2b of the CLDEQ-8
- Unacceptable contact lens fit (i.e. substantially decentered, excessive movement)

f. Study Procedures

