APPENDIX

3. Contact Lens Dry Eye Questionnaire-8 (CLDEQ-8)

Subject ID:

Date:

CONTACT LENS QUESTIONNAIRE-8 (CLDEQ-8)

1. Questions about EYE DISCOMFORT:

a. During a typical day in the past 2 weeks, **how often** did your eyes feel discomfort while wearing your contact lenses?

- 0 Never
- 1 Rarely
- 2 Sometimes
- 3 Frequently
- 4 Constantly

When your eyes felt discomfort with your contact lenses, **how intense** was this feeling of discomfort...

b. At the end of your wearing time?

Never	Not at All		Very	
have it	Intense		Intense	
0	1	2	3	4
		5		

2. Questions about EYE DRYNESS:

a. During a typical day in the past 2 weeks, **how often** did your eyes feel dry?

- 0 Never
- 1 Rarely
- 2 Sometimes
- 3 Frequently
- 4 Constantly

When your eyes felt dry, **how intense** was this feeling of dryness...

b. At the end of your wearing time?

Never	Not at All		Very	
have it	Intense		Intense	
0	1	2	3	4
		5		

3. Questions about CHANGEABLE, BLURRY VISION:

a. During a typical day in the past 2 weeks, **how often** did your vision change between clear and blurry or foggy while wearing your contact lenses?

- 0 Never
- 1 Rarely
- 2 Sometimes
- 3 Frequently
- 4 Constantly

When your vision was blurry, **how noticeable** was the changeable, blurry, or foggy vision ...

b. At the end of your wearing time?

Never	Not at All		Very	
have it	Intense		Intense	
0	1	2	3	4
		5		

4. Question about CLOSING YOUR EYES:

During a typical day in the past 2 weeks, **how often** did your eyes bother you so much that you wanted to close them?

- 0 Never
- 1 Rarely
- 2 Sometimes
- 3 Frequently
- 4 Constantly

5. Question about REMOVING YOUR LENSES:

How often during the past 2 weeks, did your eyes bother you so much while wearing your contact lenses that you felt as if you needed to stop whatever you were doing and take out your contact lenses?

- 1 Never
- 2 Less than once a week
- 3 Weekly
- 4 Several times a week
- 5 Daily
- 6 Several times a day

REFERENCES

1. Ember, Sydney. "Brands Woo Millennials With a Wink, an Emoji or Whatever It Takes." *New York Times* 28 September 2015: B1.
2. Rueff, Erin. "Contact Lens Induced Dry Eye And Binocular Vision Disorders: A Study Of Similar Symptoms." (2014): *Networked Digital Library of Theses & Dissertations*. Oct. 2015.
3. Cooper, Jeffrey S., et al. "Care of the patient with accommodative and vergence dysfunction." American Optometric Association. USA (1998): 5-10.

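### The SAP leaves period out of the 2x2 crossover models because there was no wash-out; that reason is invalid, and any week 1 to week 2 shift costs precision and, with unequal sequences, also biases the lens effect

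*SAP*

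**What the plan says.** The SAP (Statistical Methods) names a 2x2 crossover and applies a mixed model to VAS, CISS, CLDEQ, autorefraction and phoria, "allowing the sequences of each subject to be modeled as repeated measures within PROC Mixed". On period it says: "We did not have period effects since there was no gap or wash-out period between the sequences". For the lens comparison it says: "We obtained least-squares adjusted means from these and compared the difference between these as well". The significance level is 10%.

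The Protocol supplies the design:

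- Section III.a randomises 1:1 and adds: "There will be an equal number of subjects in each group".
- Section III.c randomises 30 subjects. After one week (± 2 days) "subjects will be evaluated and the alternate lenses dispensed", so there is no gap between lenses.
- The same section sets enrolment at up to 45, "allowing for up to a 33% screen failure, drop-out, or poor or missing data".
- Section III.a has the VAS completed at baseline, "at the end of day 1 and day 3 (via home diary), and at the follow-up visit at day 7".
- Section IV.c names paired t-tests for the primary outcome. These have no period adjustment either.

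**The concern.** Carry-over and period effects are different things. Carry-over is a residue of the first lens in week 2, and the lack of a wash-out makes it more of a concern. A period effect is a mean difference between week 1 and week 2 whichever lens is worn, and it can arise with or without a gap. The SAP sentence therefore fails whether it means that period was not fitted or that period effects did not exist.

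The documents make a shift possible. Subjects are enrolled with a complaint of eyestrain, so scores may regress towards the mean. The same survey is completed repeatedly. Most CLDEQ-8 items (Protocol, Appendix 3) ask about a two-week window, as in "During a typical day in the past 2 weeks", although each lens is worn for about one week. Recall at visit 2 therefore reaches back before the study, while recall at visit 3 covers both study lenses.

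Two features that might seem to deal with period do not. If the SAP's 'sequences' means the two wear periods, using them as the repeated index sets the covariance and does not estimate a mean week difference. Analysing change from baseline does not help either: there is one baseline visit, so the baseline cancels in the within-subject lens contrast.

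At stake are the precision of the primary comparison and, if the evaluable sequences are unequal, its freedom from bias.

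**Working it through.** **The plan's own figure.** The only sample-size arithmetic in the documents is the enrolment ceiling: 30 / (1 − 0.33) = 44.8, rounded up to 45, which agrees with Protocol III.c. No effect size, SD, power or week shift is given, so the inputs marked as assumed below are ranges.

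**Inputs.**
- From the documents: 30 randomised, equal groups (15/15), 10% level.
- Assumed: the 10% level is two-sided for the mixed models (the SAP says two-sided only for its t-tests), a lens effect τ of 0.5, week shifts p of 0.25, 0.5 and 1.0, and the unequal splits. The unit throughout is the SD of the within-subject lens difference.

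**Set-up.** Let D be multifocal minus single vision for one subject, coded so that benefit is positive, and p the week 2 minus week 1 shift. The mean of D is τ − p in the multifocal-first sequence (n1) and τ + p in the single-vision-first sequence (n2). N = n1 + n2.

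- *Without period:* the estimate is the mean of all D. Bias = p(n2 − n1)/N. Expected variance of D = 1 + 4·n1·n2·p² / [N(N − 1)]. Degrees of freedom N − 1.
- *With period:* the estimate is the average of the two sequence means. Bias = 0. SE = ½√(1/n1 + 1/n2). Degrees of freedom N − 2.

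**Equal sequences, 15/15.** For p = 0.5 the variance is 1 + 900 × 0.25 / 870 = 1.259, and √1.259 = 1.12. The 90% half-width is 0.348 without the term and 0.311 with it. Error rates and power below come from 200,000 simulated trials per cell.

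| Shift p | Bias | Half-width without / with | Type I error without | Power without / with |
|---|---|---|---|---|
| 0 | 0 | 0.310 / 0.311 | 10% | 85% / 85% |
| 0.25 | 0 | 0.320 / 0.311 (+3%) | 9% | 84% / 85% |
| 0.5 | 0 | 0.348 / 0.311 (+12%) | 6.6% | 80% / 85% |
| 1.0 | 0 | 0.442 / 0.311 (+42%) | 2% | 63% / 85% |

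**Unequal sequences, p = 0.5.** The table gives the size of the bias, 0.5 × |n2 − n1|/N. With the multifocal-first group larger, a shift towards improvement in week 2 gives the lower power.

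| Split | Size of bias | Type I error without | Power without (lower direction) / with |
|---|---|---|---|
| 15/13 | 0.5 × 2/28 = 0.04 | 7.0% | not tabulated |
| 15/12 | 0.5 × 3/27 = 0.06 | 7.7% | 66% / 81% |
| 15/10 | 0.5 × 5/25 = 0.10 | 10.0% | not tabulated |
| 16/14 | 0.5 × 2/30 = 0.03 | 7.0% | 74% / 85% |
| 16/12 | 0.5 × 4/28 = 0.07 | 8.5% | 64% / 82% |
| 20/10 | 0.5 × 10/30 = 0.17 | 18% | 49% / 81% |

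With the opposite shift, power without the term is 84%, 86% and 96% in the last three rows. The gain at 16/12 and 20/10 is bias in favour of the lens. At 20/10 the nominal 90% interval covers 82% of the time. With the period term, type I error is about 10% throughout.

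**Mixed-model check** (random subject, 150 data sets, p = 0.5, true effect 0.5). At 15/15 the SE is 0.202 without period and 0.178 with it. At 18/12 the mean estimate is 0.413 without and 0.518 with. Adding a sequence effect alone changes neither the estimate nor the SE.

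**The case against.** The strongest reply is that the plan as written protects itself. Thirty are randomised in equal groups, so no sequence can exceed 15. Splits of 16/14, 16/12, 18/12 and 20/10 require more than 30 randomised, or groups that were not equal. The 33% allowance also includes screen failures, which occur before randomisation and cannot unbalance the sequences. Starting from 15/15 with losses in one sequence, type I error at a 0.5 SD shift does not exceed the nominal 10%. At 15/15 the omission only makes the test conservative, and this is a pilot study.

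That stands as far as it goes: the 18% error rate belongs to an extreme case and should not carry the argument. But losses from 15/15 still bias the estimate, and at 15/12 power can drop from 81% to 66%. Nor is the ceiling of 15 firm, because obtaining at least 30 evaluable subjects after any drop-out would require randomising more than 30.

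Three further points are fair. Adaptation to the study lenses is plausible, but the documents do not mention it and the subjects already wear soft lenses. Repeated surveys and recall windows say nothing about phoria or autorefraction. The overlap of CLDEQ-8 recall at visit 3 is largely carry-over, which a period term does not cure. None of these points makes a missing wash-out a reason to leave period out.

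**Conclusion.** The concern holds. The stated reason does not support the omission, no other reason or check appears in either document, and the Protocol's paired t-test does not supply the adjustment.

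The size of the harm is unknown, because no week shift, SD or evaluable count per sequence is given. With no shift there is no harm. Under the planned equal sequences, a modest shift (0.25 SD) costs about one to two points of power and a large one (1.0 SD) about 22 points, always in the conservative direction. With unequal sequences bias is added, usually together with some excess width. It is small at mild imbalance (0.03 to 0.07 SD for a 0.5 SD shift at splits from 16/14 to 16/12) and serious only at extreme imbalance. This should be fixed: it affects the primary outcome and the remedy is cheap.

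**What to change.** Refit the VAS, CISS, CLDEQ, autorefraction and phoria models with lens, period and sequence as fixed effects and subject as random. Period may instead be the repeated index within subject, provided a fixed period effect is also fitted. Take the multifocal minus single-vision difference in least-squares means, with its 90% interval, from that model. Period is the term that matters; sequence is conventional.

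Replace the SAP's rationale sentence with a description of the refitted analysis, and give the number analysed in each sequence. State that a period term does not remove carry-over that differs by lens, and that the CLDEQ-8 recall window is open to it. Reconcile the SAP with the paired t-test in Protocol IV.c so that one primary analysis is named. Also say which measurement the SAP means by autorefraction: Protocol Table 2 schedules auto-refraction only at visit 1, while accommodative response is measured at visits 2 and 3. A period term needs a measurement from both weeks.

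The cost is one degree of freedom, at least five re-run models (more if phoria directions or test distances are analysed separately) and revised wording. If there is truly no shift, the power loss is under 0.1 point at 15/15, about 1 point at 16/12 and about 4 points at 20/10.

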Auto-refraction and keratometry	X			
CL fit assessment		X		X
Slit lamp exam with staining	X			
Tear break up time	X			
Manifest refraction ^B	X			
Distance Snellen BCVA	X			
Pupil size in dim and bright light	X			
Unilateral cover test and stereopsis	X			
Administration of CLDEQ-8, CISS, and Visual Comfort Survey	X	X		X
Ocular alignment ^C	X	X		X
Accommodative amplitude ^D	X			
Accommodative response ^E		X		X
Negative and positive relative accommodation (NRA/PRA)	X	X		X
Monocular and binocular accommodative facility ^F	X			
Study lens order randomization ^G	X			
Removal of study lens and slit lamp exam with staining		X		X
Insertion of CL and settling (15 min)	X		X	
CL fit assessment	X		X	
Distance HCHL logMAR acuity	X		X	
Exit Snellen acuity	X		X	X

BCVA = best corrected visual acuity

HCHL = high contrast high luminance

^AEntering acuity to be measured in spectacles or most recent refraction in phoropter.^BRefraction and over-refractions will be confirmed by performing red-green duochrome test. Patients will be fogged by +1.00D and the fog will be reduced in 0.25D steps until the patient reports equality, or until the last red response is reached.^CLateral and vertical heterophoria to be measured via Modified Thorington in free space at 40cm.^DMonocular push-up method with the Aston Accommodative Rule (20/30 letters at 40cm) with the subject reporting "first sustained blur" measured to the nearest one-half centimeter.^EMeasured with WAM-5500 at 25 and 40cm.^FPerformed using a +/-2.00 flipper in free space at 40cm working distance.^GTo be performed by unmasked research staff

IV. DATA ANALYSIS

a. Data Collection

All source data will be collected on paper source documents. Data will be entered into an Excel spreadsheet with double data entry to check for error before locking the data set.

b. Outcome Measures

The primary outcome is improvement of average asthenopic symptoms on digital devices as measured by a 10-question VAS repeated in-office after 1 week of lens wear. The VAS is widely used due to its simplicity and adaptability to a broad range of populations and settings. Secondary outcomes include lens preference based on a two-alternative forced choice survey and changes in CISS and CLEDQ-8 and objective measures of accommodation and binocularly.

c. Statistical Analysis

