The primary outcome measures will be assessed using paired t-tests. A chi-square will be used to assess final subject preference. Exploratory analyses may be conducted to assess trends in binocular findings, accommodative test results and symptoms, as well as to determine the appropriate sample sizes needed for future studies planned around these outcomes.

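### Two-sample t-tests between lens types for logMAR, NRA and PRA ignore that every subject wears both lenses, so real lens differences are more likely to be missed

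*SAP*

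**What the plan says.** Protocol section III.a sets the design: "This is a prospective, single site, randomized, double-masked, crossover pilot study". Section III.c has 30 subjects randomized to lens order; after about a week "subjects will be evaluated and the alternate lenses dispensed", so each subject wears both lenses.

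Table 2 schedules "Distance HCHL logMAR acuity" after lens insertion at Visit 1 (study lens 1) and again at Visit 2 in study lens 2. NRA and PRA are measured at baseline, at Visit 2 in lens 1 and at Visit 3 in lens 2. Accommodative response (WAM-5500) is also measured at Visits 2 and 3. Pupil size, accommodative amplitude and accommodative facility are measured at Visit 1 only.

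The SAP's single Statistical Methods paragraph uses a repeated-measures mixed model for VAS, CISS, CLDEQ, autorefraction and phoria. It then continues: "We also utilized two-sample two-sided t-tests when comparing certain secondary outcomes", naming pupil size, accommodation, logMAR, NRA and PRA, with the comparisons made "between lens preference at specific time points and/or between lens types". The significance level is 10%. No within-subject method is named for logMAR, NRA or PRA.

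**The concern.** A two-sample t-test assumes that the two groups of readings come from different people. For logMAR, NRA and PRA, the multifocal and single-vision readings come from the same people. The SAP wording allows two ways of comparing lenses:

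1. **Both periods pooled.** Thirty readings per lens from the same 30 subjects are treated as 60 independent readings, and the standard error is wrong.
2. **Lenses compared within one visit.** About 15 subjects in one lens are compared with about 15 others in the other lens. The standard error is valid, but no subject is compared with himself or herself.

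In either case the precision that a crossover is meant to provide is partly or wholly lost, and a real difference is more easily missed.

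This matters most for logMAR. Section III.b justifies the low add as giving an intermediate addition "without compromising distance vision as much as would be expected with higher add powers", and distance logMAR is the measurement that shows that cost. A weak test could make the multifocal look more neutral for distance acuity than the data support. Section IV.c also says exploratory analyses may be used "to determine the appropriate sample sizes needed for future studies planned around these outcomes", so an inflated standard error could carry over into later designs.

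**Working it through.** **Inputs from the documents.** 30 subjects, 1:1 lens order, one reading per lens per subject (protocol III.a, III.c, Table 2); two-sided t-tests at 10% (SAP).

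**Assumed.** The documents give no SD, effect size, power or within-subject correlation (rho) for these outcomes, so there is no stated figure to reproduce. Results are shown for rho = 0.3, 0.5 and 0.7 and for lens differences of 0.3, 0.5 and 0.8 outcome SD.

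**Standard error.** With outcome SD s and n = 30 pairs:
- true SE of the lens difference = s × sqrt(2(1 − rho)/n)
- SE used by the pooled two-sample test = s × sqrt(2/n)
- ratio = 1/sqrt(1 − rho) = 1.20, 1.41 and 1.83 at rho 0.3, 0.5 and 0.7

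The pooled test's critical value is t(0.95, 58 df) = 1.672. At rho 0.5 the observed difference must therefore exceed 1.672 × 1.41 = 2.36 true standard errors before the test rejects.

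**Type I error and power.** The pooled two-sample test was simulated on correlated normal pairs, at least 200,000 samples per setting. Paired power is from the noncentral t with 29 df and noncentrality d/sqrt(2(1 − rho)/30).

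| rho | Type I error of pooled test (nominal 10%) | Power at 0.3 SD, pooled v paired | Power at 0.5 SD, pooled v paired | Power at 0.8 SD, pooled v paired |
|---|---|---|---|---|
| 0.3 | 5.1% | 27.8% v 38.8% | 62.5% v 73.1% | 95.4% v 97.6% |
| 0.5 | 2.2% | 24.6% v 48.5% | 64.5% v 84.8% | 97.6% v 99.6% |
| 0.7 | 0.4% | 19.5% v 66.5% | 68.2% v 96.5% | 99.3% v over 99.9% |

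At 0.5 SD and rho 0.5, the chance of missing the difference rises from 15.2% to 35.5%.

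A crossover analysis with a period term has 28 df. Its power differs from the paired test by about 0.1 percentage point at most.

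**Single-visit reading, 15 v 15.** Noncentral t, 28 df, noncentrality d/sqrt(2/15): power is 21% at 0.3 SD and 38% at 0.5 SD, whatever rho is.

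**90% confidence interval half-widths at rho 0.5, in outcome SD.**
- 15 v 15: t(0.95, 28) × sqrt(2/15) = 1.701 × 0.365 = 0.62
- pooled two-sample: t(0.95, 58) × sqrt(2/30) = 1.672 × 0.258 = 0.43
- paired: t(0.95, 29) × sqrt(2 × 0.5/30) = 1.699 × 0.183 = 0.31

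**Future sample size.** Required n is proportional to the variance of the lens difference. If a later crossover were sized from the two-sample SE, n would be too large by 1/(1 − rho) = 1.4, 2.0 and 3.3 at rho 0.3, 0.5 and 0.7.

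**Direction check.** At rho 0 the two tests nearly agree (60.5% v 59.7% at 0.5 SD). Only negative rho reverses the result: at rho −0.2, type I error is 13.1% and power at 0.5 SD is 59.7% v 53.3%.

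**The case against.** The strongest objection is that the SAP does not show the error being made. One phrase covers five outcomes and two kinds of comparison, and never says that logMAR, NRA or PRA was compared by lens type with a two-sample test. Preference-group comparisons at one time point involve different subjects and are valid. A single-visit lens comparison also has a valid standard error, and if it is repeated at each visit every reading is used somewhere. Only the pooled reading gives a wrong standard error. All of this is true, and it is why the point is that the SAP allows the test. But under either reading of a lens comparison the within-subject contrast is lost, and the wording provides no alternative for these outcomes.

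Second, the outcomes carry limited weight. This is a pilot, the protocol does not list distance logMAR among its outcomes (the SAP calls it secondary), section IV.c treats accommodative findings as exploratory, and the pooled test errs on the conservative side. That limits the seriousness. It does not make a non-significant acuity result any more reassuring.

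Third, the size rests on an assumed rho, and the sample-size consequence arises only if someone uses the wrong standard error. Both are fair. Positive correlation is nonetheless the expected case for repeated measurements on one person, and the crossover design relies on it.

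Fourth, a period term goes beyond the SAP's current model, which says there were no period effects. That also stands: a paired t-test is enough to settle this point.

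**Conclusion.** The concern holds and should be fixed. For logMAR, NRA and PRA the SAP permits a between-lens test that ignores the pairing in the design, while the same paragraph keeps the within-subject structure for VAS, CISS, CLDEQ, autorefraction and phoria and gives no reason for the difference.

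For moderate differences (0.3 to 0.5 SD) and rho from 0.3 to 0.7, the pooled test gives up about 11 to 47 percentage points of power. For differences of 0.8 SD the pooled and paired tests both exceed 95%, so little is lost. These figures assume normal data, 30 complete pairs and positive rho.

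The effect is missed differences and over-wide intervals, not false claims of benefit. Not affected are the outcomes in the mixed model, the measures taken only at Visit 1 (pupil size, accommodative amplitude and facility), and preference-group comparisons at one time point. Accommodative response is exposed unless it is what the SAP means by autorefraction. The SAP does not say.

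**What to change.** - For every lens-type comparison of logMAR, NRA, PRA and any accommodation measure taken in both lenses, use the mixed-model framework already applied to VAS, preferably with lens, period and sequence as fixed effects and subject as random. The minimum is a paired t-test.
- Report each lens difference with its 90% confidence interval.
- Restrict two-sample t-tests to comparisons of preference groups at one time point.
- Add a short table giving, for each outcome, the visit, the comparison (lens type or preference) and the test. State there whether autorefraction means the WAM-5500 accommodative response.
- Base any future crossover sample size on the SD of within-subject differences.

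The cost is SAP wording and a rerun on existing data, with no new measurements. Error degrees of freedom fall from 58 to 28 or 29. Even at rho 0 that costs under 1 percentage point of power (60.5% to 59.7% at 0.5 SD).

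### For measures taken in a study lens, comparing preference groups by visit mixes the two lenses; this costs power, and biases the contrast only if preference follows lens order

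*SAP*

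**What the plan says.** The SAP (Statistical Methods) puts the VAS, CISS, CLDEQ, autorefraction and phoria into a crossover mixed model. For the rest it states: "We also utilized two-sample two-sided t-tests when comparing certain secondary outcomes". The outcomes and the first grouping are given as "pupil size, accommodation, logMAR, NRA, PRA) between lens preference at specific time points", and the full grouping reads "between lens preference at specific time points and/or between lens types". No visits are named. Nothing says that the preference comparison is made within a lens, or adjusted for lens or sequence. The level is given by "We utilized a 10% level of significance".

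The protocol (III.a) states "Subjects will be randomized in a 1:1 ratio based on a randomization schedule" and "Subjects will crossover at the second visit". Section III.c adds: "A total of 30 subjects will be randomized to begin with either multifocal or single vision distance contact lenses". Preference is asked once, at the end of the study (III.a). Table 2 shows when each measure is taken and in which lens condition.

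**The concern.** Preference is a stable label for a subject, but the lens on the eye at a given visit is set by the randomised sequence. At a fixed visit after dispensing, each preference group contains some subjects in the multifocal and some in the single-vision lens. If the lens shifts the measurement, that shift adds to the within-group spread, and a real difference between preference groups is harder to detect.

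A second harm is possible. If subjects tend to prefer the lens worn last (or first), preference is correlated with the lens worn at that visit, and part of the lens effect appears as a difference between preference groups. An order effect cannot be excluded: preference is asked only after the second lens, and the SAP says there was no washout. It is not shown either.

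**Working it through.** **1. Figures in the plan.** The documents give no SD, lens effect, preference split or power for this comparison, so there is no figure to reproduce. The only sample-size arithmetic, 30/(1 − 0.33) = 44.8, rounded up to 45 enrolled, is consistent but does not bear on this point.

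**2. Which measures are taken in a study lens (protocol Table 2).** Subjects arrive at Visit 1 without contact lenses. That the Visit 1 tests below are lens-free is inferred from their rows standing before lens insertion.

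| Measure | Visit 1 | Visit 2 | Visit 3 |
|---|---|---|---|
| Pupil size, amplitude, facility | no study lens | – | – |
| NRA/PRA | no study lens | lens 1 | lens 2 |
| Accommodative response | – | lens 1 | lens 2 |
| "Distance HCHL logMAR acuity" | lens 1, after settling | lens 2 | – |

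LogMAR has no lens-free value, so every by-visit preference test of it mixes lenses.

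**3. Formulas.** Let L be the lens effect, s the SD within one lens, and p the chance of preferring the lens worn second, with 15 subjects per sequence.
- At a visit in the second lens, a share p of multifocal-preferrers wear the multifocal, against 1 − p of single-vision-preferrers. Bias = (2p − 1)L. The sign reverses at a visit in the first lens.
- With p = 0.5 the bias is zero and the within-group SD becomes √(s² + L²/4).

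**4. Numbers put in (all assumed).** Between-subject SD 0.5 D and noise 0.25 D give s = √(0.25 + 0.0625) = 0.56 D. True preference-group difference: 0 or 0.5 D. L runs from 0.25 to 1.25 D; the top value is the maximum labelled add in protocol Table 1, used as a scale and not as a measured shift.

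By-visit SD at p = 0.5: √(0.3125 + L²/4) = 0.57, 0.61, 0.75 and 0.84 D for L = 0.25, 0.5, 1.0 and 1.25 D.

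**5. Simulation.** 40,000 trials per setting, 30 subjects, two-sided 10% t-test at the second-lens visit; Monte Carlo standard error at most √(0.25/40,000) = 0.0025.

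| L (D) | Power by visit, p = 0.5 | Power by lens, p = 0.5 | Type I by visit, p = 0.5 | p = 0.6 | p = 0.7 |
|---|---|---|---|---|---|
| 0.25 | 0.74 | 0.76 | 0.10 | 0.11 | 0.13 |
| 0.5 | 0.69 | 0.76 | 0.10 | 0.13 | 0.23 |
| 1.0 | 0.54 | 0.76 | 0.10 | 0.19 | 0.44 |
| 1.25 | 0.46 | 0.76 | 0.10 | 0.21 | 0.51 |

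The by-lens test holds type I error at 0.10 throughout. Example of bias: p = 0.6 and L = 1.0 D give (1.2 − 1) × 1.0 = 0.2 D.

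**6. Check in SD units.** Dioptres do not carry over to logMAR, so the same question was run with s = 1 and a true difference of 0.8 SD. With preference unrelated to lens order, the unadjusted test has power 0.68, 0.65, 0.59 and 0.43 at lens effects of 0, 0.5, 1 and 2 SD; adjusting for the lens worn gives about 0.66 at each. With no true difference, type I error is 0.11, 0.14 and 0.20 (0.5, 1 and 2 SD) if 60% prefer the lens worn at that visit, and 0.15, 0.26 and 0.48 if 70% do.

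**The case against.** The strongest reply is that the SAP sentence is ambiguous. The words after the time points also name lens types, so the preference groups may have been compared within each lens. That reading is possible. But the wording equally allows a separate lens comparison, or a by-visit comparison alone, and a reader cannot tell which was done. The ambiguity softens the charge but does not remove the need to correct the text.

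Other points stand in part:
- **Scope.** Pupil size, amplitude, facility and Visit 1 NRA/PRA involve no lens mix. A reader might infer that the whole SAP list is affected; Table 2 does not support that.
- **Accommodation.** The SAP puts autorefraction in the crossover model, yet Table 2 schedules auto-refraction at Visit 1 only. The SAP's term may therefore mean the instrument-measured accommodative response (footnote E). If so, that outcome already has a crossover analysis, and the exposed set is logMAR and NRA/PRA at Visits 2 and 3.
- **Bias.** A reader might infer that differences between preference groups merely reflect the lens worn that day. That needs preference to depend on lens order, and neither document says it does. With p = 0.5, type I error stays at 10%.
- **Size.** At a lens effect of 0.25 D the loss is about 2 points of power.
- **Stakes.** This is a pilot, and protocol IV.c treats trends in binocular and accommodative findings as exploratory.

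**Conclusion.** The point holds for measures taken in a study lens: logMAR at Visits 1 and 2, NRA/PRA at Visits 2 and 3, and accommodative response if it is among the t-tested outcomes. For these, a t-test by visit, as the SAP's wording allows, is a weaker test than one by lens, and nothing in the SAP guarantees the better version.

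The loss of power is negligible for a small lens effect and material from about 1 SD upward: 7 points at 0.5 D (0.5/0.56 = 0.9 SD) and 30 points at 1.25 D (1.25/0.56 = 2.2 SD). Inflated false positives are conditional: 0.11 to 0.21 if 60% prefer the lens worn second, 0.13 to 0.51 if 70% do, and none if preference is unrelated to order. Every SD, lens effect and preference share here is an assumption. The documents do not support a claim that any particular preference finding is an artefact, and the primary VAS analysis is unaffected.

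**What to change.** For each outcome in the t-test list, state the visit and the lens condition, and say what accommodation refers to. Then:
- **Measures in a study lens:** compare preference groups within lens type, once on the value in the multifocal and once on the value in the single-vision lens. Alternatively, fit one repeated-measures model with terms for preference, lens and period. A by-lens comparison pools the two periods, so the model is preferable if a period effect is a concern.
- **Lens-free Visit 1 measures** (pupil size, amplitude, facility, baseline NRA/PRA): keep the plain two-sample tests.

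The cost is SAP wording and a re-sort of existing data by lens instead of by visit. Each scheduled in-lens measure has one value per lens, so no new data are needed and no subjects are lost. The downside is slightly more analysis and a few more contrasts at the 10% level, which should be reported as exploratory.
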